**REFERENCES**

**STUDY SCHEMA: Phase III Multicenter Randomized Controlled Clinical Trial**

\* TS/SCP = treatment summary and personalized survivorship care plan given to all intervention and control study participants.

## 1.0 INTRODUCTION

This document is a Phase III clinical research protocol and the described study will be conducted in compliance with the IRB approved protocol, associated Federal regulations and all applicable IRB requirements.

This study proposes that predictable health surveillance and unmet emotional needs of adult hematopoietic cell transplantation (HCT) survivors can be improved through a centralized, cost and resource-sparing, national program that optimizes health informatics and provides online expertise and stepped care telehealth assistance with using the program when necessary. If successful, this project would provide long-term HCT survivors and their providers with a patient-centered program to facilitate managing their emotional and health care needs. Long-term HCT survivors do not receive adequate care for their unique health and emotional needs due to lack of knowledge and resources to manage these needs in their home communities, although many of these needs have been well defined. Lack of access to care increases premature morbidity and mortality in HCT survivors particularly for cardiovascular and metabolic disease (cardiometabolic) and subsequent malignancies.

Among adult long-term cancer survivors, those who received HCT have a 9-fold increased risk of mortality related most commonly to cancer recurrence, subsequent malignancy s and cardiovascular diseases.[2-5] They are also at risk for poorer psychosocial health including cancer-related distress, with depression at higher levels than age-matched norms.[6-8] By focusing on HCT survivors who are 2-5 years after treatment, we target a high risk group and build upon our previous experience delivering tailored online content with telehealth/phone based stepped care for those who do not improve at an interim assessment point at 6-weeks after randomization.

The major goal of this protocol is to test the efficacy of the integrated, tailored online site, using a self-management model of care that distributes survivorship care plans, tools and resources for management of distress and health care adherence directly to cancer survivors as the coordinators of their own health. Our previous research has demonstrated efficacy in reducing depression and distress with survivors at a single site[9, 10], at six sites across the nation[11], and has tested the efficacy of providing a survivorship preventive care plan{4855}[10] With this protocol we will retain the focus on depression, distress and health behaviors, while improving the methodology by adding telehealth stepped care and leveraging the data registry and assessment infrastructure at the Center for International Blood and Marrow Transplant Research and the National Marrow Donor Program (CIBMTR/NMDP) for post-study sustainable implementation of the program. The protocol also builds on increasing recognition that a single online device or method will not meet the needs of all survivors.

Although HCT is often considered distinct from other cancer treatments, the primary outcomes in the proposed research are also some of the most prevalent concerns and causes of mortality in other groups of survivors treated with standard therapy.[12, 13] The methods we propose are relevant for any survivors who would benefit from cost and resource conserving interventions provided by online and telehealth modalities. With these improvements and the extension of the intervention to twelve transplant centers we expect to strengthen both the reach and efficacy of the intervention tested in protocols 2258 and 2605, while we advance the science of delivering health behavior change models of care to cancer survivors.

This protocol is a 12-site multicenter RCT (N=492), with Seattle as the prime site, partnering with transplant centers in Ohio, Minnesota, Wisconsin, Michigan, Massachusetts, Pennsylvania, New York, Florida, Kansas, Illinois, and Texas. This provides age, region and rural/urban diversity. Participants randomized to the intervention will receive immediate access to the tailored online program, with options for social-media, adding stepped care self-management calls for those not improving by a 6-week interim assessment for those in group 1. Control participants will receive access to a website that provides annotated links to publicly available HCT and cancer websites as well as delayed internet site access. Outcomes will be assessed at 6 weeks, 3 months and 12 months.

## 2.0 BACKGROUND

Among adult long-term cancer survivors, those who received HCT live with some of the highest risks for life-threatening chronic health conditions including cardiovascular disease, diabetes, osteoporosis, and recurrence or second cancers along with other risks. Even more prevalent in HCT survivors are psychological symptoms that inhibit quality of life, specifically depression and cancer-related distress. Many survivors have residual complications in specific domains with resultant impact on quality of life (QOL.)[14]. Survivors have more difficulty after transplant if they struggle with chronic GVHD, have pulmonary disease, infection or other psychological or medical complications. [15-17]

### Significance and Gaps This Project Will Fill

Despite their rapidly expanding numbers, survivors more than 5 years after HCT have been understudied both in defining their needs and in addressing long term complications through RCTs. This protocol extends our knowledge of long term or late effects while testing treatment to reduce common problems that have not resolved on their own. A major impediment to addressing needs of HCT survivors is their dispersion around the country, in areas lacking transplant-related expertise. Online methodologies will allow us to enroll difficult to access survivors and will provide otherwise unavailable expertise and evidence-based guidelines for care. With this internet, social-media and telehealth program, we optimize flexibility to respond at the readiness and at the time convenience of participants in a highly cost-effective modality since adding participants adds minimal cost. We believe the program could improve standards of care and health outcomes for HCT survivors and address a major gap in care for these geographically dispersed survivors.

**Cancer-Related Emotional Distress and Depression.** Cancer-related distress is a significant problem for HCT and other with a negative impact on quality of life.[6, 18] Distress is far more prevalent than clinical depression, with prevalence estimated at 43% in long-term HCT survivors and moderate to severe depressive symptoms in 13-15%. [7, 19-21] Distress can be due to many factors such as uncertainty, cGVHD, managing the side effects of transplant, and financial stress.[22-24] Our preliminary research found that 41% of 2-5 year HCT survivor study participants had elevated distress on the Cancer and Treatment Distress (CTXD) measure.[25] In the cohort of 936 study participants, all but 1% of those with elevated depression scores also had elevated distress on the CTXD, suggesting that the CTXD captures a large proportion of depressive symptoms.[11] Therefore, we believe our focus on CTXD distress as the primary outcome will also address depression needs for nearly all survivors, although we will still measure depressive symptoms as a secondary endpoint. Risk factors for distress for allogeneic HCT include younger age, shorter time after HCT, and cGVHD. For autologous HCT, comorbidities are a risk factor for distress.[26, 27] Pre-HCT depression predicts later depression and other poorer outcomes[6, 27] as well as survival.[6, 28, 29] We have demonstrated that the INSPIRE online program for HCT survivors can improve distress (see 2.2 Preliminary Research). Others have demonstrated improved distress and post-traumatic stress in HCT survivors with telehealth cognitive behavioral treatment.[30]

**Cardiovascular Disease (CVD) and Metabolic Syndrome.** With a risk of premature CVD related death increased 2.3- 4.0-fold compared to the general population,[31, 32] HCT survivors are more likely to develop adverse CVD risk factors leading to development of metabolic syndrome (constellation of high triglyceride levels, low HDL-cholesterol, hypertension, high fasting glucose and increased waist circumference) which predisposes individuals to early CVD-related death. Insulin resistance is the primary pathophysiologic mechanism and HCT survivors are more likely to develop hypertension, hyperlipidemia, and diabetes.[33-36] In the Bone Marrow Transplant Survivor Study we examined diabetes, hypertension, and CVD events in 2+ year HCT survivors (n=1089) and found that allogeneic HCT survivors were 3.6 and 2.0 times more likely to report diabetes and hypertension compared to siblings. In addition, exposure to TBI increased the risk of diabetes 3.4 times.[37] In a case-control study of 1379 HCT survivors compared to 509 randomly selected individuals from the general population, the 10-year cumulative incidence of ischemic heart disease, cardiomyopathy, stroke, and all-cause death from CVD ranged from 3.5-6.0%. [38] Other mechanisms include cardiomyopathy and coronary artery damage due to chemotherapy and chest irradiation.[38-43] Most cardiometabolic abnormalities can be screened for and treated. Screening and preventative recommendations for CVD in HCT survivors have been recently published by a combined US and European task force.[44]

**Subsequent Malignancy Risk.** As the leading cause of non-relapse late mortality, subsequent malignancies after HCT are one of the most significant long-term health risks. Numerous studies report the risk of a subsequent malignancy between 4 to 11-fold higher than in the general population.[45-51] The types of subsequent malignancies seen vary over time with earlier occurrence for myelodysplasia/acute myeloid leukemia and post-transplant lymphoproliferative disorders and longer latency for solid tumors.[52] The cumulative incidence of subsequent malignancies increases with longer length of follow-up, approaching 8.8% at 20 years after HCT, and no evidence of a plateau.[49] Risks of subsequent malignancies after HCT are increased for skin, thyroid, oral cavity, esophagus, liver, breast, nervous system, bone and connective tissues,[46-48, 53] and risk factors include total body irradiation (TBI), young age at HCT, cGVHD and prolonged immunosuppression.[54] HCT survivor specific guidelines have been published taking these into account,[54] and form the basis for the recommendations in the SCP that will be utilized for this study.[55-58]

**Treatment Summary & Survivorship Care Plan (SCP).** SCPs are recommended for all cancer survivors, and should include the following information: (1) cancer type, treatments and their potential long term effects, (2) information about screening and preventive evaluations and their timing, and (3) recommendations about lifestyle practices.[59, 60] When used in shared decision making as a cornerstone of self-management, SCPs may increase communication between oncologists and primary care providers.[61] A majority of cancer programs face barriers to implementing delivery of SCPs (time and effort to create and disseminate) and thus are not providing them.[62-66] Having a written plan may help survivors more than just talking with them about their SCPs.[67, 68] Health informatics reduces barriers to generating SCPs.[69, 70] We are designing this protocol with dissemination in mind as has been recommended when using SCPs.[71] To date, research testing delivery of a printed SCP, without follow-up to personalize the application of the information to the individual, has not found positive outcomes with regard to health care adherence (HCA) or distress, although survivors may report feeling positive about having received SCPs.[65, 72-84] Personalizing an action plan for the individual through online interaction, and follow-up to address barriers by telehealth if needed, are necessary to make SCPs more effective.[85, 86]

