### Self-Management Theory

Self-Management has been used to help patients cope with their chronic diseases (e.g., diabetes) and has been influencing cancer survivorship.[1, 90, 95, 131] Foster and colleagues developed an online intervention to assist survivors in self-managing fatigue.[132] Self-management has been used in cancer survivors to increase physical activity and improve diet,[133] and to reduce distress.[134] In a meta-analysis of online self-management studies, small to moderate effect sizes were found for anxiety, depression and quality of life.[89] Younger survivors expect that at least some of their self-management will occur online.[135] Self-management is a central premise of online interventions that attempt behavior change (see Figure 1.2 for our planned model of self-management).[136]

**Stepped Care Using Telehealth.** HCT survivors are amenable to using telehealth calls.[30, 137] One stepped care intervention was found to be comparable to usual care, but the study was done in the pre-transplant setting and enrolled patients with low distress.[138] Telehealth has been as effective as face-to-face interventions for cancer survivors.[139] Our first INSPIRE program found that PST using 8 phone calls in addition to the online intervention, compared with the online program alone or delayed access control, was more effective than online alone for distress.[10] However, we found great variety in the chosen targets for PST, such that it was difficult to measure outcomes, and many survivors did not feel a need for the extended telehealth calls. For the stepped care methodology, we are using a self-management model we have tested with young adult cancer survivors, with 3 phone calls and content focused on achieving goals specific to the study endpoints of distress, cardiac and/or subsequent malignancy HCA, and retaining an emphasis on specifying personal goals and anticipating barriers and facilitators to reaching goals.

This protocol tests an intervention to reduce common problems after HCT that have not resolved by two years after treatment, while extending our knowledge of risks for long-term or late effects in these survivors. It builds on prior online intervention research, with broad reach and high utilization. If efficacious in this multi-center RCT, it can be disseminated nationwide with limited maintenance costs.

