### Primary Aims

1. Determine whether 2-5 year HCT survivors with elevated cancer-related distress or poor health care adherence, adherence to cardiometabolic or subsequent malignancy surveillance who are randomized to receive the online, patient-centered, self-management stepped care program will report reduced distress, and improved health care adherence for cardiometabolic or subsequent malignancy surveillance at 12 months when compared with an active control group who receive access to HCT survivorship best practices.
2. Determine characteristics of intervention participants who require telehealth stepped care at 6-weeks because they 1) do not meet criteria for adequate knowledge of subsequent malignancy and cardiometabolic risks, or 2) do not report improved distress, or 3) have not logged in to the online program.
3. Determine resources that would be needed to sustain the intervention as a national HCT survivorship program if implemented through the CIBMTR//NMDP.

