### 7.0 PLAN OF TREATMENT

#### Intervention Selection and Approach

The CIBMTR data registry contains 3765 potentially eligible 2-5 year survivors including 14% minorities from the 13 participating centers. The study Biostatistician will develop a Statistical Analysis Software (SAS) program for random selection of potentially eligible participants with oversampling of minorities (initially all eligible minority cases will be approached) until a minimum of 15% of those randomized are minority race or

ethnicity. The remaining non-minority survivors will be randomly ordered. Each participating center will be sent their randomized approach lists in blocks of 25 cases. Based on our previous INSPIRE enrollment experience with similar eligibility, we found that 26% of cases were not eligible after further screening. We project that we will enroll and randomize 51% of eligible non-minority survivors and 40% of minority survivors. Thus we expect we will approach approximately 1358 (36%) of potentially eligible cases, with 26% not eligible after approach, to achieve our total projected enrollment N=492 to the randomized study.

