### Cost and Resource Tracking

We will track the costs of maintaining the program if disseminated (not including elements required for research implementation) as indicated by 1) materials, 2) programming for site maintenance, technical problem solving, and updating content and maintaining social networking, 3) multi-center staff time for identifying, approaching and tracking participants, and responding to participant comments 4) coordinating center and CIBMTR/NMDP staff time for tracking participants, responding to participant comments and requests, and responding to technical problems. We will track costs separately for the self-management call component. Site staff will report cost summaries quarterly. These will be standardized to report the cost per participant who reaches at least one of the primary endpoints for the study, specified for each type of cost (materials, staff time) as well as total costs. Because we will track the costs of preparing SCPs and internet links provided to the control group and will know their outcomes, we will also be able to calculate an incremental cost-effectiveness ratio for the internet intervention program compared to the control cost-effectiveness, similar to the method described by Mandelblatt and colleagues.[171, 172]

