This is a descriptive aim defining costs and resource requirements. Data relevant to resource utilization (costs) and methods of collection are described in section 8.3 Cost and Resource Tracking. All costs associated with the intervention and, separately, the control arms of the study for the Group 0 and Group 1 subjects in the study will be summed and standardized to per person costs. We will use these amounts to calculate an incremental cost ratio for the online intervention program and telehealth intervention component compared to the control cost, similar to the method described by Mandelblatt et al.[171, 172] The costs of maintaining the various components of the program, relative to their use, will be calculated separately for those in the Group 0 and 1 intervention arms, specific to maintaining the social media site, the internet program, and the telehealth calls (Group 1 only) relative to the number of participants using those components among intervention participants.

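### Aim 3 asks what a national program would need, but its analysis ends at trial-volume average costs, with no fixed/per-participant split, national volume or projection

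*Combined protocol and SAP*

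**What the plan says.** Section 3.1 lists as the third primary aim: "Determine resources that would be needed to sustain the intervention as a national HCT survivorship program", if implemented through the registry organizations. Section 12 repeats it under the secondary hypotheses and again in the Aim 3 plan.

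Cost and Resource Tracking (8.4 in the table of contents; the Aim 3 plan cites it as 8.3) sets out what is collected. It covers the cost of maintaining the program if disseminated and leaves out research elements. There are four items: materials; programming, content and social networking; multi-center staff time; and coordinating-center and registry staff time. Calls are tracked separately, and sites report quarterly. Costs are then "standardized to report the cost per participant who reaches at least one of the primary endpoints", by type of cost as well as in total, and an incremental cost-effectiveness ratio against control is foreseen.

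The Aim 3 plan says "This is a descriptive aim defining costs and resource requirements". Costs of each arm "will be summed and standardized to per person costs", and an incremental cost ratio against control follows. Costs of the social media site, the internet program and the calls are each related to the number of intervention participants who use them.

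On how cost behaves with volume, the documents offer only two general statements. Section 2.1 describes delivery "in a highly cost-effective modality since adding participants adds minimal cost", and the self-management section says that, if efficacious, "it can be disseminated nationwide with limited maintenance costs".

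**The concern.** The aim is a question about a national program, and the planned outputs are averages at the size of the trial. An average cost carries over to another volume only if every cost grows in proportion to participants. The protocol's own premise is that cost does not grow that way, at least for the website.

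Two readings of the results are at stake. First, a sponsor who takes the trial's per-person cost as the national one would get a figure that depends on how many people the trial happened to enrol, and would still lack an annual budget or staffing requirement. Second, the comparison of online and telehealth components would shift with volume. Coach time is spent per participant and does not dilute; site maintenance largely does.

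**Working it through.** **Plan's own figure.** There is none to reproduce: the documents give no cost, fixed share or national volume. The one nearby figure that can be checked agrees: 1,358/3,765 = 36.1%, stated as 36%.

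**Inputs from the documents**
- 492 randomized. With equal allocation (an assumption, consistent with the equal per-arm numbers in Power Calculations), n = 492/2 = 246 in the intervention arm.
- Section 7.0: "The CIBMTR data registry contains 3765 potentially eligible 2-5 year survivors", at the participating centers. These are listed cases, not users.
- Section 7.0: 26% of cases ineligible on further screening, and about 1,358 approached to reach 492.
- Section 7.6: three to four calls, 20–30 minutes for the first and 10–20 for each booster.

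**Assumptions.** f is the share of per-person cost at trial volume that is fixed (not given, so varied from 0.1 to 0.9). Cost is linear: fixed total F plus v per participant.

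**Formula.** Average cost at volume N is F/N + v. Relative to the trial average at n it is (1 − f) + f·n/N. The overstatement is the reciprocal, 1/[(1 − f) + f·n/N].

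**Volumes**
- Upper illustration: N = 3,765, treating every listed case as an eligible user. 246/3,765 = 0.0653.
- After ineligibility and uptake: 3,765 × 0.74 = 2,786. Uptake is 492/(1,358 × 0.74) = 0.49, and 2,786 × 0.49 = 1,365. 246/1,365 = 0.1802.

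| f | N = 3,765 | N = 1,365 |
|---|---|---|
| 0.1 | 1/0.9065 = 1.10 | 1/0.9180 = 1.09 |
| 0.2 | 1/0.8131 = 1.23 | 1/0.8360 = 1.20 |
| 0.5 | 1/0.5327 = 1.88 | 1/0.5901 = 1.69 |
| 0.8 | 1/0.2523 = 3.96 | 1/0.3442 = 2.91 |
| 0.9 | 1/0.1588 = 6.30 | 1/0.2622 = 3.81 |

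**Sensitivity.** If fixed cost is spread over all 492, because controls get delayed access, the values at N = 3,765 are 1.77, 3.28 and 4.60 for f = 0.5, 0.8 and 0.9. For very large N the ratio tends to 1/(1 − f), which is 2, 5 and 10 for the same f.

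**Per-participant component.** Three calls take 20 + 2×10 = 40 to 30 + 2×20 = 70 minutes of coach time. Four take 20 + 3×10 = 50 to 30 + 3×20 = 90. This is per stepped-care participant at any volume.

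**Can the split be recovered from what is collected?** Only in part. The programming item is largely fixed, and materials and calls are largely per participant. The two staff-time items are mixed. The multi-center item combines identifying and approaching survivors with tracking and answering participants, and these follow different counts. The coordinating-center item combines participant contact with technical problem solving.

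**The case against.** The other side has real strength. Cost and Resource Tracking already takes the dissemination perspective, excludes research costs, itemises by type, promises totals and tracks calls separately, and the Aim 3 plan keeps the three components apart. So it would be wrong to infer that the plan reports nothing but trial-scale ratios. One qualification is that the sentence on totals can be read as totals per success rather than a budget.

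A reader might also infer that the protocol calls the program mostly fixed cost. It does not. The two statements on cost are general background, and the plan contains much work that grows with volume: mailed care plans, coached calls, and staff time to approach, track and answer participants.

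Nor can one conclude that the trial figure will badly overstate national cost. The fixed share is unknown, and at 10–20% the overstatement is only 1.1- to 1.2-fold at either volume. The 3,765 is a stock of potentially eligible survivors at participating centers, not an annual count of users, and 1,358 is the number approached.

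Finally, Aim 3 is descriptive, the plan nowhere equates per-person trial cost with national cost, and within-trial ratios are ordinary outputs. The economic methods it cites are not available here, so how they handle scale cannot be judged.

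These points limit the size and tone of the criticism. They do not close the gap: itemised costs are inputs, and no stated step turns them into a national resource requirement.

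**Conclusion.** The mismatch stands. Followed as written, the Aim 3 analysis does not deliver what the aim asks for, because it names no volume, separates no fixed cost and projects nothing. The direction of error is certain for any fixed cost above zero and any volume above the trial's. The size is not: about 1.1- to 6.3-fold at 3,765 users for fixed shares of 10% to 90%, and about 1.2- to 3.8-fold at 1,365 users for 20% to 90%. These figures assume equal allocation, linear cost, and volumes built from the participating centers' registry count. They ignore time, although maintenance cost accrues by year. A true national volume could be larger. No efficacy analysis, error rate or power calculation is affected.

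**What to change.** 1. In Cost and Resource Tracking, have the quarterly report code each item as fixed per year or per participant. Split the staff-time items into approach, participant contact and technical work. Do this prospectively, because pooled time may be hard to divide afterwards.
2. In the Aim 3 plan, make these the main results: annual fixed cost and staff time; variable cost per enrollee; cost per call series times the observed stepped-care rate; and projected total and per-person annual cost at stated numbers of users per year, with a range.
3. Keep the trial per-person cost and incremental ratio, labelled as specific to the trial's size. While editing, reconcile the two sections: one uses cost per success and a cost-effectiveness ratio, the other cost per person and a cost ratio.

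The cost is one extra code on an existing quarterly form and a short projection table. No new data source or change to trial conduct is needed.
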